### **10.2 Reporting procedures for All Adverse Events**

All AEs occurring during the study observed by the investigator or reported by the participants, whether or not attributed to study, will be recorded on the CRF.

The following information will be recorded: description, date of onset and end date, severity, assessment of relatedness to study, other suspect device and action taken. Follow-up information should be provided as necessary.

AEs considered related to the study as judged by a medically qualified investigator or the sponsor will be followed until resolution or the event is considered stable. All related AEs that result in a participant's withdrawal from the study or are present at the end of the study, should be followed up until a satisfactory resolution occurs.

It will be left to the investigator's clinical judgment whether or not an AE is of sufficient severity to require the participant's removal from the study. A participant may also voluntarily withdraw from treatment due to what he or she perceives as an intolerable AE. If either of these occurs, the participant must undergo an end of study assessment and be given appropriate care under medical supervision until symptoms cease or the condition becomes stable.

The severity of events will be assessed on the following scale: 1 = mild, 2 = moderate, 3 = severe.

The relationship of AEs to the study will be assessed by a medically qualified investigator.

### **10.3 Reporting Procedures for Serious Adverse Events**

All SAEs, must be reported to the Sponsor within one working day of discovery or notification of the event. The Sponsor will perform an initial check of the information and ensure that it is reviewed at the next R&D Management meeting. All SAE information must be recorded on an SAE form and sent to the Sponsor using the appropriate reporting form and the contact details on there. Additional information received for a case (follow-up or corrections to the original case) needs to be detailed on a new SAE form which must be sent to the Sponsor using the appropriate reporting form and the contact details on there.

The Sponsor will report all SUSARs to the Research Ethics Committee concerned. Fatal or life-threatening SUSARs must be reported within 7 days and all other SUSARs within 15 days. The CI will inform all investigators concerned of relevant information about SUSARs that could adversely affect the safety of participants.

In addition to the expedited reporting above, the CI shall submit once a year throughout the study or on request an Annual Report to the Ethics Committee which lists all SAEs / SUSARs that have occurred during the preceding 12 months.

Only SAEs that occur during the fTCD study will be reported to the sponsor. After this, the Patient or Volunteer, ceases to be involved in the study.

## **11. STATISTICS**

### **11.1 Statistical analysis**

The null hypothesis being tested is that:

- (a) cerebral haemodynamic parameters, including CBFv and ARI, and any alterations related to the performance of the ACE-III Cognitive Examination are not significantly different between MCI, VascD, AlzD patients and HC subjects.

All normally distributed continuous variables will be described as mean (SD) and continuous variables with skewness as median (IQR). Comparison between baseline data for MCI patients, VascD patients, AlzD patients and HC will be made using Student t-tests for normally distributed data, or by appropriate non-parametric test, with Bonferroni correction applied to multiple comparisons. Repeated measures ANOVA will be adopted to test for the effect of performance of the ACE-III Cognitive Examination on CBFv and ARI between MCI patients, VascD patients, AlzD patients and HC subjects.

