## **7. ELIGIBILITY CRITERIA**

### **7.1 Overall Description of Trial Participants**

Patients with MCI, Patients with VascD and Patients with AlzD, together with age-, gender- and BP matched healthy volunteer control subjects (HC) will be recruited to enable the complete data analysis of 11 MCI Patients, 11 VascD Patients, 11 ALzD Patients and 11 HCs.

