### **11.2 Sample size calculation**

A formal sample size calculation was not possible for this study therefore a realistic number of participants has been selected based on previous experience of similar research studies by [name], [name] and [name].

However, to detect a change of 2 units in autoregulation Index (ARI) and to calculate the required sample size we followed the technique as previously described by others (Brodie FG et al, 2009). For this study a sample of 11 patients per intervention group will allow the detection of a difference between groups (MCI patients, VascD patients, AlzD patients and HC subjects) in the ARI of 2 units with 80% power at the 5% significance level.

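### Holm's step-down correction would recover a small part of the power that plain Bonferroni gives up in the baseline group comparisons, at the same 5% family-wise bound

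*Combined protocol and SAP*

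**What the plan says.** Section 11.1 (Statistical analysis) has two separate sentences on group comparisons.

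- The first is on baseline: "Comparison between baseline data for MCI patients, VascD patients, AlzD patients and HC will be made using Student t-tests for normally distributed data", or by a suitable non-parametric test, "with Bonferroni correction applied to multiple comparisons". It names neither the baseline variables nor the family of comparisons.
- The second assigns the effect of performing the ACE-III on CBFv and ARI to a repeated measures ANOVA. It names no follow-up comparison and no correction.

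The null hypothesis in the same section covers haemodynamic parameters, including CBFv and ARI, as well as their task-related changes. Section 8.4 provides a 5-minute resting recording, so resting values will exist. Section 8.3 also uses the word baseline for demographic data.

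Section 11.2 says that a formal calculation was not possible. It then states that "a sample of 11 patients per intervention group will allow the detection of a difference between groups" of 2 ARI units, with "80% power at the 5% significance level". It gives no SD ("we followed the technique as previously described by others") and mentions no correction for multiplicity. Section 7.1 plans recruitment "to enable the complete data analysis of 11 MCI Patients, 11 VascD Patients, 11 ALzD Patients and 11 HCs".

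**The concern.** With 11 per group, any two-group comparison is weak, and dividing alpha by the number of comparisons weakens it further. Bonferroni applies the full divisor to every p-value. Holm uses the full divisor only for the smallest p-value. After each rejection it divides by the number of hypotheses still untested. Every Bonferroni rejection is therefore also a Holm rejection, and the family-wise error stays at or below 5% under any dependence.

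When all six pairs of four groups are tested, Shaffer's version goes further. If one pair truly differs, at most three of the equalities can still be true, so the divisors fall to 6, 3, 3, 3, 2, 1.

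What is at stake is how well the study can say which diagnostic groups differ at rest. If the baseline tests instead serve to check matching, the correction works against their purpose, because it makes imbalance harder to see.

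**Working it through.** **Inputs.** From the documents: 11 per group, four groups, 5% level, 80% power, 2 ARI units (sections 7.1 and 11.2). Assumed, because the documents do not say: two-sided tests; the SD of ARI; and a family of six pairs, or three contrasts with controls.

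**The plan's own figure.** It cannot be reproduced independently without an SD, so the SD was solved for.

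- Normal approximation: n = 2(1.960 + 0.842)² SD² / 2². Setting n = 11 gives SD = 1.67.
- Two-sample t-test: 80% power at n = 11 needs SD = 1.59, so d = 2/1.59 = 1.26 (1.256 unrounded).

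Eleven per group therefore fits one uncorrected two-group comparison if the SD is about 1.6 to 1.7.

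**Power of one comparison after Bonferroni.** Non-centrality = d√(n/2) = 1.256 × √5.5 = 2.95, with 20 df.

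| Level | Critical t | Power |
|---|---|---|
| 0.05 | 2.086 | 80% |
| 0.05/3 = 0.0167 | 2.613 | 63% |
| 0.05/6 = 0.0083 | 2.927 | 52% |

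**Step-down methods, six pairs.** Simulation with pairwise t-tests on 20 df, 100,000 data sets per pattern, true difference 1.256 SD.

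| Pattern of means | Measure | Bonferroni | Holm | Shaffer |
|---|---|---|---|---|
| Two groups against two | power per true pair | 52% | 58% | 61% |
| | all four true differences found | 18% | 29% | 29% |
| | at least one found | 85% | 85% | 85% |
| One group against three | power per true pair | 52% | 55% | 60% |
| | all three true differences found | 27% | 33% | 38% |
| | at least one found | 77% | 77% | 77% |
| Two groups midway, extremes 1.256 SD apart | power for the extreme pair | 52% | 53% | 54% |

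**Three contrasts with controls.** Power per true contrast rises from 63% (Bonferroni) to 67% with Holm if two contrasts are real, and to 72% if all three are.

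**Error control.** Simulated family-wise error stayed at or below 4.5% for all three methods in every scenario. With two groups against two it was 1.6% for Bonferroni, 2.9% for Holm and about 3.4% for Shaffer.

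**Range over the unknown SD (six pairs, 2 ARI units).** At SD 1.2, Bonferroni gives 82% and Holm 85–87%. At SD 2.0, the figures are 31% and 33–34%.

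**If the tests are a matching check.** An imbalance of 0.8 SD reaches significance with 43% power uncorrected and 18% at 0.05/6.

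**The case against.** The strongest reply is that Bonferroni is valid, prespecified and conventional, so this is a matter of efficiency. That stands, and it sets the grade of the point. Four stronger readings are tempting, and the documents or the figures do not support them.

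- **That the correction weakens the main analysis.** The primary objective (5.1) concerns CBFv during the ACE-III, and 11.1 tests that effect by repeated measures ANOVA. The Bonferroni clause belongs to the baseline sentence, so changing it leaves the ANOVA as it is.
- **That Holm restores the lost power.** Holm's first step is the Bonferroni test, so the chance of finding at least one difference is practically unchanged. Bonferroni loses 80 − 52 = 28 points per pair. Holm returns between 1 and 6 of them in the patterns examined.
- **That Bonferroni buys nothing.** Both methods meet the 5% bound, but Bonferroni's actual error is lower when some differences are real (1.6% against 2.9%). It also has simple simultaneous intervals.
- **That all six pairs of resting CBFv and ARI are known to be the family.** This is a plausible inference from the four-group wording, the null hypothesis and the resting recording. The plan does not say so.

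Holm is also not the only alternative. For normal data with a pooled variance, single-step Tukey gives about 61% per pair, raises the chance of finding at least one difference from 85% to 89%, and keeps simultaneous intervals. Its drawback is that 11.1 also allows non-parametric tests. Holm works on any valid p-values and so fits the existing sentence.

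Finally, one may say that the silence of 11.2 on any correction matters more than the choice between Bonferroni and Holm. That is fair. It is a separate matter, which neither method resolves.

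**Conclusion.** The point holds in a limited form. For baseline haemodynamic comparisons, plain Bonferroni is dominated by Holm at the same 5% family-wise bound. The size is modest: about 1 to 6 points of power per pair with Holm, up to about 9 with Shaffer's divisors, and roughly 6 to 11 points in the chance of finding every true difference in the two-against-two and one-against-three patterns. With three control contrasts the gain is 4 to 9 points per contrast.

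These figures rest on an assumed difference of 1.26 SD, two-sided tests, 11 complete participants per group and an assumed family. That Holm never rejects less than Bonferroni needs none of these assumptions. It is an optional, low-cost improvement and not a correction of an error.

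**What to change.** In section 11.1:

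1. State which baseline variables are compared between groups, and name the family for each: all six pairs, or the three contrasts with healthy controls.
2. For baseline haemodynamic variables such as resting CBFv and ARI, replace the Bonferroni correction with Holm's step-down correction, applied to the t-test or non-parametric p-values. Shaffer's divisors (6, 3, 3, 3, 2, 1) are an option if all six pairs of one variable are tested.
3. For demographic and matching variables, report group differences as standardised differences in place of corrected tests.

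The cost is a sentence or two, with no extra participants or data. The downside is that step-down tests have no simple matching simultaneous confidence intervals, so unadjusted or Bonferroni intervals should be shown beside the adjusted p-values and labelled as such. Section 11.1 does not currently promise simultaneous intervals, so nothing already planned is lost.

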**2. SYNOPSIS**

Study Title	Cerebral Haemodynamic Changes During Cognitive Testing: A Functional Transcranial Doppler (fTCD) study
Internal ref. no.	
Trial Design	Prospective, observational, case-control study
Trial Participants	Healthy Control Subjects, Patients with Mild Cognitive Impairment, Patients with Vascular Dementia and Patients with Alzheimer’s Dementia
Planned Sample Size	11 Healthy Control Patients, 11 Patients with Mild Cognitive Impairment, 11 Patients with Vascular Dementia and 11 Patients with Alzheimer’s Dementia
Follow-up duration	None
Planned Trial Period	7 Months
Primary Objective	To compare the beat-to beat cerebral blood flow velocity (CBFv) between patients with Mild Cognitive Impairment (MCI), patients with Vascular Dementia (VascD), patients with Alzheimer’s Dementia (AlzD) and age-, gender- and blood pressure (BP)-matched healthy control (HC) subjects during performance of the Addenbrooke’s Cognitive III (ACE-III) examination
Secondary Objectives	
 
1) To investigate whether performance of the Addenbrooke’s Cognitive III Examination is associated with differences in other beat-to-beat cerebral haemodynamic parameters, specifically autoregulation index (ARI), between MCI patients, VascD patients, AlzD patients, and age-, gender- and BP-matched HC subjects.
 
2) To assess the acceptability and feasibility of this protocol in patients with cognitive impairment in clinical practice.
 
3) To assess the reproducibility of measurements in cognitively impaired patient group at 3 months from initial measurement
 

Outcome Measure	
This is not an intervention study, and therefore it would not be appropriate to assess the classical primary and secondary outcome measures such as death and disability for this study. However, we intend to evaluate the following relevant outcomes:
 
 
1. The percentage of recruited subjects (HC, MCI patients, VascD patients and AlzD patients) able to comply with the full measurement protocol.
 
2. The percentage of measurements rejected because of aspects related to data quality during the analysis protocol, with recorded reasons.
 
3. Overall, the percentage of recruited subjects (healthy controls, MCI patients, VascD patients and AlzD patients) in whom values for the following parameters can be derived:
 

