### **6.2 Primary and Secondary Endpoints/Outcome Measures**

This is not an intervention study, and therefore it would not be appropriate to assess the classical primary and secondary outcome measures such as death and disability for this study. However, we intend to evaluate the following relevant outcomes:

- 1) The percentage of recruited subjects (HC, MCI patients, VascD patients and AlzD patients) able to comply with the full measurement protocol.
- 2) The percentage of measurements rejected because of aspects related to data quality during the analysis protocol, with recorded reasons.
- 3) Overall, the percentage of recruited subjects (healthy controls, MCI patients, VascD patients and AlzD patients) in whom values for the following parameters can be derived:
  - % change of CBFv at baseline in response to performance of the ACE-III Cognitive Examination
  - Autoregulation index (using the Tiecks model and from the phase, gain and coherence).

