### **8.7 Discontinuation/Withdrawal of Participants from Study Treatment**

Each participant has the right to withdraw from the study at any time and without giving a reason. A decision to withdraw at any time, or a decision not to take part, will not affect the standard of care that participant receives. In addition, the investigator may discontinue a participant from the study at any time if the investigator considers it necessary for any of the following reason:

- An inability to comply with study procedures
- Consent withdrawn
- Loss of capacity

In the case of withdrawal in the healthy control group, they will be replaced to ensure that there are 11 healthy control subjects with complete data analysis.

All of the above will be recorded in the case report form (CRF).

Prior to the study, we will ensure that the participant is aware that he/she is free to withdraw from the study at any time for any reason. However, should this situation occur we would like to keep all the health information and data that has been collected so far for the final analysis. This will be clearly stated in both the Participant (Patient and Volunteer) Information Leaflet and Participant (Patient and Volunteer) Consent Form.

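### The only between-group test during the ACE-III is a repeated-measures ANOVA that in its classical form needs complete data; losses are expected, and the allowance for them is unquantified and covers only some cases

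*Combined protocol and SAP*

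**What the plan says.** **Analysis.** Section 11.1 states: "Repeated measures ANOVA will be adopted to test for the effect of performance of the ACE-III Cognitive Examination on CBFv and ARI", compared between the four groups. It names no repeated level and gives no rule for a missing one. The t-tests in the same section are for baseline data.

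**Expected losses.** Section 6.2 makes incompleteness an outcome: the share of subjects "able to comply with the full measurement protocol", and "The percentage of measurements rejected because of aspects related to data quality during the analysis protocol". It also counts the participants in whom ARI and the percentage "change of CBFv at baseline in response to performance of the ACE-III Cognitive Examination" can be derived. No expected rates are given.

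**Recordings.** Section 8.4 describes four per participant: one baseline recording and three blocks of ACE-III tasks, with both middle cerebral arteries (MCAs) insonated.

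**Numbers.** The Synopsis plans "11 Healthy Control Patients, 11 Patients with Mild Cognitive Impairment, 11 Patients with Vascular Dementia" and the same number with Alzheimer's dementia. Section 7.1 says recruitment is "to enable the complete data analysis of 11 MCI Patients, 11 VascD Patients, 11 ALzD Patients and 11 HCs". Section 11.2 says "a sample of 11 patients per intervention group will allow the detection of a difference between groups" of 2 ARI units with 80% power at the 5% level. Section 8.7 replaces healthy controls who withdraw and mentions no other replacement. Of participants who withdraw it says "we would like to keep all the health information and data that has been collected so far for the final analysis".

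**The concern.** The primary objective (section 5.1) is to compare CBFv between groups during the ACE-III, and this ANOVA is the only test named for it. Classical repeated-measures ANOVA drops a participant who lacks any one level, along with that participant's good recordings. The protocol itself expects such gaps, in a session of about 90 minutes that includes cognitively impaired patients.

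At 11 per group, each loss matters. If it is not replaced, power falls. If it is replaced to meet section 7.1, more people are needed than the Synopsis plans, and the analysed patients may be those better able to finish. With neither the level nor the counting rule fixed, the analysed population for the main comparison could be settled after the rejections are known.

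**Working it through.** **1. The plan's own figure.** Section 11.2 gives 11 per group for 2 ARI units, 80% power and 5%, but no SD, so it cannot be reproduced independently. Solving backwards with a two-sided two-sample t-test, 11 v 11 has 80% power at d = 1.256, so SD = 2/1.256 = 1.59. Other tests imply SDs from 1.23 to 2.13. No inflation for loss is visible. At SD 1.59, power is 76% for 10 v 10 and 71% for 9 v 9. This is only a guide, because 11.1 keeps t-tests for baseline data.

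**2. Inputs for the ANOVA.** From the documents: four groups of 11 (Synopsis) and four recordings (8.4). Assumed, because the documents give nothing: a rejection rate r of 5% or 10% per recording, either independent or clustered within person (beta-binomial, intraclass correlation 0.3).

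**3. Complete participants if the level is the recording (k = 4).**
- Independent: share = (1 - r)^4.
- Clustered: share = product over i = 0 to 3 of (a + i)/(s + i), with s = 1/0.3 - 1 = 2.333 and a = (1 - r)s. At 5%: 0.9500 x 0.9650 x 0.9731 x 0.9781 = 0.873.
- Usable recordings discarded = 1 - share/(1 - r).
- Recruits needed for 11 complete = 11/share, rounded up.

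| r | Clustering | Share complete | Of 11 | Usable recordings discarded | Recruits per group |
|---|---|---|---|---|---|
| 5% | none | 0.815 | 9.0 | 14% | 13.5, so 14 |
| 5% | 0.3 | 0.873 | 9.6 | 8% | 12.6, so 13 |
| 10% | none | 0.656 | 7.2 | 27% | 16.8, so 17 |
| 10% | 0.3 | 0.757 | 8.3 | 16% | 14.5, so 15 |

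Over four groups, replacement means 52 to 56 recruits at 5% and 60 to 68 at 10%, against 44 planned. If both MCAs also enter as levels (8 cells), 5% leaves 11 x 0.95^8 = 7.3 (independent) to 11 x 0.821 = 9.0 (clustered).

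**4. Power of group-by-recording if losses are not replaced.** With full data the degrees of freedom are 3 x 3 = 9 and 40 x 3 = 120. One group's task response is shifted equally at all task levels, by the amount that gives 80% power with full data (noncentral F, sphericity assumed). Power is then averaged over simulated patterns of rejection.

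| r | Clustering | Complete cases | All usable recordings |
|---|---|---|---|
| 5% | none | 67% | 76% |
| 5% | 0.3 | 72% | 76% |
| 10% | none | 55% | 72% |
| 10% | 0.3 | 63% | 72% |

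The last column treats participant effects as fixed, so it uses within-person information only. A repeat of the simulation agreed to within about one percentage point.

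**5. If the level is only baseline v task.** A person with one of two levels missing adds nothing within-person, so both methods give the same power (74% to 75% at 5%, if each level is lost at rate r). If task is averaged over whichever of the three task recordings survive, a person is lost only when the baseline fails or all three task recordings fail:
- 5%: 0.95 x (1 - 0.05^3) = 0.950, or 10.4 of 11.
- 10%: 0.90 x (1 - 0.10^3) = 0.899, or 9.9 of 11.

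Clustering at 0.3 changes these only to 10.4 and 9.8.

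**The case against.** The best defence is section 7.1. It sets the 11 as participants with complete data in every group, so a reader who infers that the plan makes no allowance for loss goes too far. If recruitment continues until 7.1 is met, the stated power is kept. This stands, and it makes the power losses above conditional. What remains is that the allowance has no number, the Synopsis plans exactly 11, and the only written replacement rule covers controls who withdraw. Patient groups, and recordings rejected later at off-line analysis, are not covered.

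Three other strong readings are tempting, and the documents do not support them:
- **That the plan orders incomplete participants to be discarded.** Section 11.1 states no deletion rule. Deletion follows from the classical form of the method, and the plan is silent.
- **That section 8.7 contradicts the ANOVA.** Data kept after withdrawal can still serve the baseline tests and the percentages in 6.2. They just cannot enter this test in its classical form.
- **That the 5-37% inadequate-window rate in section 8.2 is the rejection rate.** That check comes before any recording is made, so it does not measure recordings rejected afterwards.

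It is also fair to say that baseline v task fits the percentage-change measure in 6.2 best, and there the mixed model gains essentially no power. In addition, section 8.4 puts a one-minute baseline at each end of every task recording, so for CBFv a lost baseline recording need not lose the change from baseline. Whether that is long enough for ARI is not stated. These points limit the gain. They do not remove the need to name the level and write the rule.

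**Conclusion.** The concern holds in a limited form. The named test suits complete data, the protocol expects incomplete data, and neither the missing-data rule nor the recruitment allowance is written down for all groups.

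The size depends on the unnamed level. With four recordings and no replacement, complete-case power is about 67-72% at 5% rejection and 55-63% at 10%, against about 76% and 72% when all usable recordings are used. With replacement, power holds and the cost is about 2 to 3 extra recruits per group at 5% and 4 to 6 at 10%, plus possible selection of people able to complete, whose size cannot be derived. For baseline v task, the power gain is essentially nil.

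The rejection rates, the clustering, sphericity and the effect shape are all assumptions. The documents give no CBFv variance, so actual power for CBFv cannot be computed. This is a cheap improvement to the method; it does not show that the study is underpowered.

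**What to change.** **Section 11.1.** Name the repeated level. Replace repeated-measures ANOVA with a linear mixed model:
- random participant effect;
- fixed effects of group, task level and group-by-task;
- side as a within-participant factor if both MCAs are analysed;
- a small-sample degrees-of-freedom correction such as Kenward-Roger.

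Use all usable segments, including partial records from participants who withdraw. Keep the complete-case ANOVA as a sensitivity analysis.

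**Sections 7.1 and 8.7.** State, for all four groups, whether a participant with a rejected recording counts towards the 11.

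**Reporting.** Give the participants and segments contributing to this test in each group.

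**Cost.** Protocol wording and slightly more modelling work, with no new visits or measurements. The mixed model assumes that missing segments are explained by the observed data (missing at random). That may fail if more impaired patients are the ones who do not complete.
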